1.0 Research Design

1.1 Purpose/Specific Aims

The purpose of this study is to explore the efficacy of Aggrenox (Dipyridamole ER 200mg and Aspirin 25mg), in brand or generic formulation, in patients with SARS-CoV-2 infection with symptoms consistent with COVID-19. For ease, we will identify the drug as Aggrenox, regardless of the formulation.

Among 132 SARS-CoV-2 patients (66 patients in each randomized arm), we will determine the efficacy of Aggrenox on clinical outcomes.

A. Endpoints:

Primary Endpoint:

Change in composite COVID ordinal scale at day 15. Ordinal scale: 1) not hospitalized with resumption of normal activities; 2) not hospitalized, but unable to resume normal activities; 3) hospitalized, not requiring oxygen; 4) hospitalized, requiring oxygen; 5) hospitalized, requiring high-flow oxygen therapy, or noninvasive ventilation; 6) hospitalized, requiring invasive ventilation; 7) ventilation plus additional organ support such as vasopressors, renal replacement therapy and ECMO and 8) death.

Secondary Endpoints:

- 1) all-cause mortality assessed on day 15 and day 28.
- 2) oxygen-free days through day 28.
- 3) invasive-ventilator-free days through day 28.
- 4) ICU-free days through day 28.
- 5) hospital-free days through day 28.
- 6) increase in cycle threshold (Ct) of SARS-CoV-2 PCR test as an approximation of decline in viral load at days 7 and 15.
- 7) decrease in the markers D-dimer/ ferritin/ c-reactive protein at days 7 and 15.
- 8) thromboembolic complications including stroke at day 28.
- 9) Change in COVID ordinal scale at day 28.
- 10) When feasible urine will be analyzed for markers of tubular injury IL-18, kidney injury molecule-1 [KIM-1], neutrophil gelatinase-associated lipocalin [NGAL]), inflammation (monocyte chemoattractant protein-1 [MCP-1]), and repair (human cartilage glycoprotein-40 [YKL-40]

B. Hypotheses / Research Question(s)

Compared to standard care, addition of Aggrenox (Dipyridamole ER 200mg/ Aspirin 25mg), to standard care will result in improvement in composite COVID ordinal scale at day 15. Additionally, combined Aggrenox (Dipyridamole ER 200mg/ Aspirin 25mg orally/enterally), and standard care will reduce need for ventilation, length of mechanical ventilation, hospital length of stay, ICU length of stay and improve survival more than standard care alone in SARS-CoV-2 patients.

1.2 Research Significance

Coronavirus disease 2019 (COVID-19) is caused by severe acute respiratory syndrome coronavirus 2 (SARS-CoV-2) and which has recently evolved into a pandemic posing a serious

RUTGERS

Rutgers, The State University of New Jersey [name]

threat to public health worldwide.^{1,2}. Thus, development of effective preventative and therapeutic interventions is paramount.

Despite its importance, information about pathologic mechanisms of SARS-CoV-2 remains incomplete. Recent data suggests the role of exaggerated immune/inflammatory response and hypercoagulability as pathogenic mechanisms leading to clinical manifestations such as acute respiratory distress syndrome (ARDS), stroke and extrapulmonary multiorgan dysfunction.³ Due to the significant activation of coagulation system, the coagulopathy associated with COVID-19 may result in thromboembolic complications such as deep venous thrombosis, pulmonary embolism and strokes.⁴

Prophylactic anti-coagulation therapies have become the standard of care in the management of these patients.⁴ The International society of thrombosis and hemostasis has recommended that all COVID-19 patients admitted to the hospital, irrespective of the severity of their illness, should be started on prophylactic dose of low molecular weight heparin (LMWH).⁵ The Society of thrombosis and haemostasis research also recommended that all hospitalized COVID-19 patients should receive pharmacological venous thromboembolism (VTE) prophylaxis unless contraindicated.⁶ Recent literature shows that the risk of thromboembolism is higher in patients admitted to the ICU. For the patients admitted to the ICU or having additional risk factors for VTE such as BMI> 30mkg/m2, history of VTE or rapidly rising D-dimer levels, high-risk prophylactic LMWH dosages twice daily should be considered.⁶ The *therapeutic* doses of either UFH or LMWH should be considered for those who have confirmed thrombosis including filter thrombosis.⁷ The anti-inflammatory properties of LMWH have been suggested to provide additional benefits in COVID-19 patients.⁴

Utilization of a therapeutic that can simultaneously intervene along multiple pathways (viral replication, inflammation, vasoconstriction, and coagulation) can dramatically improve patient outcomes.

Adenosine is a highly potent immunoregulatory nucleoside that interferes with inflammatory processes by modulating the biosynthesis and release of proinflammatory cytokines, slowing down the oxidative activity, preventing platelet aggregation, and reducing neutrophils adhesion and degranulation. ^{8,9} One mechanism to increase extracellular adenosine is to inhibit intracellular uptake of adenosine and thereby capitalize on its anti-inflammatory properties. It has a wide-ranging effects on multiple organ systems by interacting with different adenosine receptors. ⁹ Equilibrative nucleoside transporters (ENTs) are nucleoside transporters that regulate the flux of endogenous nucleosides, nucleobases and therapeutic analogs. ¹⁰ Given the critical nature of regulating nucleosides in a number of pathological processes, ENTs have emerged as a druggable target. ENT inhibitors are used to modulate nucleosides in a number of disease states including viral infections such as HIV¹¹, and tumors¹².

Dipyridamole (DIP) is one such ENT inhibitor (specific for the major and ubiquitous nucleoside transporter ENT-1), that inhibits nucleoside (adenosine) uptake into the endothelial and other cells and has been shown to enhance the anti-inflammatory and immunomodulatory effect of adenosine. A recent study has shown that DIP increases extracellular adenosine levels and thereby provides a significant decrease in CD8+T-cell activation and decreased macrophage activation among persons with HIV-1 infection on antiviral therapy. 11

DIP may have additional therapeutic advantages to SARS-CoV-2 patients. DIP is a widely known *phosphodiesterase (PDE) inhibitor with antiplatelet*¹⁴ *and vasodilatoratory*¹⁵ *effects*. Of particular note, a recent screen of FDA approved drugs identified the ability of DIP to *effectively*

Protocol Title: ATTAC-19 – Aggrenox To Treat Acute Covid-19 Pro#2020001469

Rutgers, The State University of New Jersey [name]

suppress SARS-CoV-2 replication with a therapeutically achievable EC50 concentration of 100 nM.¹⁶ Moreover, a small study of 22 COVID-19 patients suggested improved outcomes including reduction in coagulation markers.¹⁷ These antiviral data are not without precedent as DIP has also been shown to have powerful antiviral activity against single-stranded RNA viruses in vitro, and in a VSV-induced viral pneumonia model in vivo.¹⁶-²⁰ Additional possible benefits could include the anti-inflammatory action and promotion of mucosal healing.²¹ It may also prevent acute injury and progressive fibrosis of the lung, heart, liver, and kidney.²²² In one small clinical series of 12 patients (pre-print, not peer-reviewed data), the authors used DIP as a prophylactic anti-coagulation therapy and reported significantly increased platelet and lymphocyte counts and decreased D-dimer levels in comparison to control patients. Two weeks after initiation of DIP therapy 60% of their severe patients and all patients with mild disease were discharged from the hospital.¹⁷

Aspirin is a well-known anti-platelet drug with anti-inflammatory properties. Aspirin inhibits platelet cyclooxygenase-1 activity that is essential for generation of thromboxane A2. Thromboxane A2 is a potent vasoconstrictor that also induces platelet aggregation and release of proinflammatory proteins from platelet storage granules. The literature evidence suggests that aspirin plus extended-release dipyridamole may be more suitable for preventing secondary stroke because, in addition to their antiplatelet actions, these drugs possess complementary anti-inflammatory properties.²³

Thus, we hypothesize that Aggrenox (Dipyridamole ER 200mg/ Aspirin 25mg orally/enterally), adjunctive therapy can be useful for SARS-CoV-2 infected patients through enhancing immune recovery, antiviral properties, and correcting the coagulation profile.

We propose a randomized, 2-arm, open-label single-site pilot study to evaluate the effect of oral/enteral Aggrenox on clinical outcomes in patients with SARS-CoV. We will randomly assign 132 consenting participants to two treatment groups: 1) Aggrenox (Dipyridamole ER 200mg/Aspirin 25mg orally/enterally), + standard care and 2) standard care alone. We will collect demographic, clinical, laboratory and radiological data. The patients would be followed daily for 2 weeks after enrollment while the patient is in the hospital and once discharged, they will be called every 3rd day to follow up on the symptoms.

1.2 Research Design and Methods

1: 1 Randomized design.

Arm 1: Aggrenox plus standard care. Participants will receive Aggrenox (Dipyridamole ER 200mg/ Aspirin 25mg orally/enterally), 2 times daily (FDA–recommended dose) starting on the day of enrollment for a total of 2 weeks along with standard care.

Arm 2: Standard care. Participants will receive standard care starting on the day of enrollment for a total of 2 weeks.

We will perform a randomized, 2-arm, open-label single-site pilot study to evaluate the effect of oral Aggrenox (Dipyridamole ER 200mg/ Aspirin 25mg orally/enterally), on clinical outcomes in patients with SARS-CoV-2. In this research proposal, we will randomly assign 132 consenting participants with diagnosis of SARS-CoV-2 to two treatment groups: 1) Aggrenox (Dipyridamole ER 200mg/ Aspirin 25mg orally/enterally) + standard care and 2) standard care alone. Participants will be screened, enrolled, receive treatment and followed for 28 days. The study

Protocol Title: ATTAC-19 – Aggrenox To Treat Acute Covid-19 Pro#2020001469

Rutgers, The State University of New Jersey [name]

aim and procedure will be explained to every eligible subject and informed consent will be obtained from interested subjects or authorized proxy to participate in the study. We do not anticipate problems with enrollment as sufficient number of COVID-19 patients are admitted at Rutgers-NJMS (approximately 2-5 new COVID-19 admissions daily, and total 18-20 patients who are currently admitted at Rutgers-NJMS with 5-6 patients in intensive care units).

Randomization. The P.I. or study coordinator will review the screening and enroll participants in the randomization. Once a participant has been randomized, we will conduct all evaluations irrespective of whether the participant starts the treatment, and how long the participants continues on the treatment or not. SARS-CoV-2 patients will be allocated in a 1:1 randomized fashion using computer generated random sequence to one of two groups: the Aggrenox (Dipyridamole ER 200mg/ Aspirin 25mg orally/enterally), plus standard care or the standard care. Data collection will end after 28 days, or the patient dies or withdraws consent.

A. Research Procedures

Study Procedures:

Day 0 – Screening Visit: (Complete baseline COVID Case report form – Appendix B: Module 1)

- o Review eligibility criteria
- o Obtain informed consent for trial enrollment
- o Demographic data
- o Medical history
- o Physical examination will be performed as part of the routine care and will be abstracted from the medical record
- o Vital signs (blood pressure, heart rate, temperature) will be abstracted from the medical record
- o Electrocardiogram will be performed as part of the routine care and will be abstracted from the medical record
- o Labs: CBC, BMP, Coagulation profile, Ferritin, D-Dimer, CRP. will be collected as part of the routine care and will be abstracted from the medical record
- o Concomitant medications (starting from the time the patient signs the informed consent)
- o Collection of research samples:
 - Saliva, oral, nasal, and pharyngeal swabs, and sputum (if spontaneously producing sputum or intubated) for SARS-CoV-2 RNA will be collected at baseline day 0
- Randomize study participant through RedCap.

Treatment Period –Days 1 - 14 (Complete daily COVID Case report form – Appendix B: Module 2)

- Clinical assessment completed by Research Nurse. May be conducted by phone if the patient is discharged before 14 days.
 - Review of daily temperatures
 - Review of medication compliance
 - Adverse events

Protocol Title: ATTAC-19 – Aggrenox To Treat Acute Covid-19 Pro#2020001469

Rutgers, The State University of New Jersey [name]

- Record standard of care treatments and/or procedures prescribed
- Labs: At day 7 and day 14: we will abstract CBC, BMP, Coagulation profile, Ferritin, D-Dimer, CRP results from the medical record.

Collect research specimens:

- Saliva, oral, nasal, and pharyngeal swabs, and sputum (if spontaneously producing sputum or intubated) for SARS-CoV-2 RNA will be collected at day 7 and day 14 in a subset of patients.
- Urine samples will be collected on day 1 and day 14.

Treatment Period –Days 15 - 28 (Complete daily COVID Case report form – Appendix B: Module 2)

- Clinical assessment completed by Research Nurse. May be conducted by phone if the patient is discharged before 14 days.
 - Review of daily temperatures
 - Adverse events
 - Record standard of care treatments and/or procedures prescribed
 - COVID ordinal outcomes scale on day 28.

Discharge/ Death: Complete COVID Case report form –(Appendix B: Module 3)

Treatment Plan:

Participants will be randomized 1:1 to Aggrenox or standard treatment.

- Active Comparator: (Aggrenox (Dipyridamole ER 200mg/ Aspirin 25mg orally/enterally).
 Participants will receive Aggrenox (Dipyridamole ER 200mg/ Aspirin 25mg orally/enterally), 2 times daily (FDA–recommended dose) starting on the day of enrollment for a total of 2 weeks + standard care.
- Standard care Comparator: Participants will receive standard care starting on the day of enrollment for a total of 2 weeks.

2. Subject Enrollment

- 1. Patients who are eligible for the study will be enrolled in the clinical trial after they or their authorized proxy provide informed consent for study participation. A copy of the institution's IRB approved informed consent will be on file RedCap. The patients will be enrolled through RedCap, the Clinical Trials Management System for this study. Contact the Rutgers Clinical Trials Unit, if you have any questions about the Registration/Enrollment process.
- Registration: Any subject that has signed the consent will be entered into RedCap. A Copy of the consent will be uploaded into the Documents section.
- Enrollment: Once eligibility has been confirmed, the completed, signed and dated eligibility checklist will be uploaded into the Documents section. RedCap will randomize the patient and a sequence number (subject study ID) will be generated at the time of enrollment, this is the point the patient is considered on study.

Protocol Title: ATTAC-19 – Aggrenox To Treat Acute Covid-19 Pro#2020001469

Rutgers, The State University of New Jersey [name]

Patients will not start protocol treatment prior to registration.

3. Study Safety Assessments

The Principal Investigator is responsible for ensuring that all staff involved in the study are familiar with the content of this section.

Definitions:

Adverse Events:

An adverse event is the development of an undesirable medical condition or the deterioration of a pre-existing medical condition following or during exposure to a pharmaceutical product, whether considered causally related to the product. An undesirable medical condition can be symptoms (e.g. nausea, chest pain), signs (e.g. tachycardia, enlarged liver) or the abnormal results of an investigation (e.g. laboratory findings, electrocardiogram). In clinical studies, an AE can include an undesirable medical condition occurring at any time, including run-in or washout periods, even if no study treatment has been administered. The term AE is used to include both serious and non- serious AEs.

Serious Adverse Events:

A serious adverse event is an AE occurring during any study phase (i.e., screening, run- in, treatment, wash-out, follow-up), at any dose of the study drugs that fulfills one or more of the following criteria and deemed secondary to the use of study drug:

- Results in death
- Is immediately life-threatening
- > Requires in-patient hospitalization or prolongation of existing hospitalization
- Results in persistent or significant disability or incapacity
- > Is a congenital abnormality or birth defect
- Is an important medical event that may jeopardize the patient or may require medical intervention to prevent one of the outcomes listed above.
- 1.1.1 The causality of SAEs (their relationship to all study treatment/procedures) will be assessed by the investigator(s) and communicated to Boehringer Ingelheim (BI) via BI SAE form and the FDA via MedWatch form, if applicable.

Causality will be reported as either "Yes" or "No".

- Yes: There is a reasonable causal relationship between the investigational product administered and the AE.
- ➤ No: There is no reasonable causal relationship between the investigational product administered and the AE.

2. Recording of Adverse Events

Rutgers, The State University of New Jersey [name]

Non-serious adverse events and SAEs will be determined from the time the patient is enrolled into the study and up to and including the 2 weeks follow-up period (after the completion of 2 weeks of treatment with Aggrenox) for a total of 28 days . All grade 3 or higher AEs will be recorded. Grade 1-2 AEs do not need to be recorded. After withdrawal from treatment, subjects must be followed-up for all existing and new AEs for 14 calendar days after the last dose of trial drug and/or until event resolution. All new AEs occurring during that period must be recorded (if SAEs, they must be reported to the DSMB and Rutgers IRB as per SOPs.). AEs will be recorded per Rutgers IRB SOPs. The common terminology criteria for adverse events (CTCAE) will be used as a reference to grade the adverse events.

(https://ctep.cancer.gov/protocoldevelopment/electronic_applications/docs/CTCAE_v5_Quick_R eference_8.5x11.pdf (Accessed on March 09, 2018)

All study-related adverse events/ SAEs must be followed until resolution, unless in the Treating Investigator's opinion, the condition is unlikely to resolve due to the patient's underlying disease.

3. Reporting of Serious Adverse Events

Investigators and other site personnel must inform the Rutgers IRB per the SOPs on the required forms. FDA will be informed per SOP, via a MedWatch, of any serious or unexpected adverse events that occur in accordance with the reporting obligations of 21 CFR 312.32. It is the responsibility of the principal investigator to compile all necessary information and ensure that the FDA receives a report according to the FDA reporting requirement timelines.

In addition to FDA, the Sponsor shall report all SAEs and non-serious AEs that occur ,throughout the treatment period and up to and including the 2 weeks follow-up period (after the completion of 2 weeks of treatment with Aggrenox) for a total of 28 days which are relevant for a reported SAEs and any AEs relevant to a reported SAE by fax or other secure method using BI IIS SAE form to the BI Unique Entry Point in accordance with timeline specified in the safety data exchange agreement .

For each adverse event, the investigator will provide the onset date, end date, causality, intensity, treatment required, outcome, seriousness, and action taken with the investigational drug.

The investigator does not need to actively monitor patients for adverse events once the clinical trial has ended. However, if the investigator becomes aware of an SAE(s) that occurred after the patient has completed the clinical trial (including any protocol specified follow-up period), it should be reported to BI if investigator considers it as relevant to the BI study drug.

All SAEs meeting the criteria for expedited reporting will be reported to the Rutgers IRB within the mandated time frames. All SAEs within the safety follow-up window (e.g., within 14 days after the last dose of study medications) established in the protocol will be reported.

Non-serious adverse events and SAEs will be collected from the time the patient is enrolled into the study, throughout the treatment period and up to and including the 2 weeks follow-up period (after the completion of 2 weeks of treatment with Aggrenox) for a total of 28 days. After withdrawal from treatment, subjects must be followed-up for all existing and new AEs for 14 calendar days after the last dose of trial drug and/or until event resolution. All new AEs

Protocol Title: ATTAC-19 – Aggrenox To Treat Acute Covid-19 Pro#2020001469

Rutgers, The State University of New Jersey [name]

occurring during that period must be recorded (if SAEs, then they must be reported to the FDA as per their reporting criteria). All study-related toxicities/ SAEs must be followed until resolution, unless in the Treating Investigator's opinion, the condition is unlikely to resolve due to the patient's underlying disease.

Clinical Safety Assessments

Recording of Adverse Events

Non-serious adverse events and SAEs will be determined from the time the study drug is given, throughout the treatment period and up to and including the 2 weeks follow up period. All grade 3 or higher AEs will be recorded. Grade 1-2 AEs do not need to be recorded. After withdrawal from treatment, subjects must be followed-up for all existing and new AEs for 14 calendar days after the last dose of trial drug and/or until event resolution. All new AEs occurring during that period must be recorded (if SAEs, they must be reported to the DSMB and Rutgers IRB as per SOPs.). AEs will be recorded per Rutgers IRB SOPs.

Adverse Events Based on Signs and Symptoms

When collecting AEs, the recording of diagnoses is preferred (when possible) to recording a list of signs and symptoms. However, if a diagnosis is known and there are other signs or symptoms that are not generally part of the diagnosis, the diagnosis and each sign or symptom will be recorded separately.

Vital Signs

Temperature will be obtained at least two times a day (AM and PM). Nursing staff will record the temperature while the patient is in the hospital. Body temperature will be measured in degrees Fahrenheit using an automated thermometer. An automated thermometer will be provided to the patient once discharged from the hospital for checking the temperature at least once a day for the study duration (28 days total from the enrollment day).

Study Efficacy/Response Assessments

Change in composite COVID ordinal scale at day 15. Ordinal scale: 1) not hospitalized with resumption of normal activities; 2) not hospitalized, but unable to resume normal activities; 3) hospitalized, not requiring oxygen; 4) hospitalized, requiring oxygen; 5) hospitalized, requiring high-flow oxygen therapy, or noninvasive ventilation; 6) hospitalized, requiring invasive ventilation; 7) ventilation plus additional organ support such as pressors, renal replacement therapy and ECMO and 8) death.

Other response criteria used as secondary endpoints include the need of invasive ventilation, the days dependent on ventilator, hospital free days, thromboembolic complications, COVID ordinal scale at day 28 and mortality.

Data Points

Case Report Forms²⁴

Completion of the electronic case report forms (eCRFs) will be done in accordance with the instructions outlined in the study specific data capture plan. All eCRFs are considered the primary data collection document for the study and are stored in RedCap in a confidential

Protocol Title: ATTAC-19 – Aggrenox To Treat Acute Covid-19 Pro#2020001469

Rutgers, The State University of New Jersey [name]

format. Only key personnel who are delegated in the delegation of authority log are permitted to make entries, changes, or corrections in the eCRF. All users of RedCap will complete user training, as required or appropriate per regulations. An audit trail will be maintained automatically by the electronic CRF management system.

Data Points to be collected:

- Baseline medical history
- Treatment compliance
- Daily temperatures
- Symptoms of disease
 - Adverse events
 - Concomitant medications
 - Any standard of care treatments or procedures to manage COVID-19

Data Submission Timeline and Forms

Completion of eCRFs will occur within 72 hours of study time point unless otherwise indicated. Baseline (pre-study) eCRFs (e.g., enrollment, medical history, concomitant medications, etc.) will be completed no later than 24 hours after the start of treatment.

Study Duration: Study participants will be treated for fourteen (14) days and will then remain on follow-up for up to 4 weeks (28 days) total from their enrollment. The study will end for each subject upon the completion of their day 28 post enrollment follow-up interview.

The study will be conducted over approximately 24 months: 6-8 months for enrollment and follow-up/data collection and 18 months for specimen processing and analysis, and data analysis.

We will account for all the patients registered in the study. The number of patients who were not evaluable, who died or withdrew before treatment was completed will be specified. The distribution of follow-up time will be described and the number of patients lost to follow-up will be given.

B. Endpoints

Primary endpoint:

Change (as compared to baseline on day 0) in composite COVID ordinal scale at day 15 Ordinal scale: 1) not hospitalized with resumption of normal activities; 2) not hospitalized, but unable to resume normal activities; 3) hospitalized, not requiring oxygen; 4) hospitalized, requiring oxygen; 5) hospitalized, requiring high-flow oxygen therapy, or noninvasive ventilation; 6) hospitalized, requiring invasive ventilation; 7) ventilation plus additional organ support such as vasopressors, renal replacement therapy and ECMO and 8) death.

Secondary endpoints:

- 1) all-cause mortality assessed on day 15 and day 28.
- 2) oxygen-free days through day 28.
- 3) invasive-ventilator-free days through day 28.

Protocol Title: ATTAC-19 – Aggrenox To Treat Acute Covid-19 Pro#2020001469

Rutgers, The State University of New Jersey [name]

- 4) ICU-free days through day 28.
- 5) hospital-free days through day 28.
- 6) increase in cycle threshold (Ct) of SARS-CoV-2 PCR test as an approximation of decline in viral load at days 7 and 15.
- 7) Change in the inflammatory markers D-dimer/ ferritin/ c-reactive protein at days 7 and 15 as compared to baseline on day 0.
- 8) thromboembolic complications including stroke at day 28.
- 9) Change (as compared to baseline on day 0) in COVID ordinal scale at day 28.
- 10) if feasible urine will be analysed for markers of tubular injury IL-18, kidney injury molecule-1 [KIM-1], neutrophil gelatinase-associated lipocalin [NGAL]), inflammation (monocyte chemoattractant protein-1 [MCP-1]), and repair (human cartilage glycoprotein-40 [YKL-40]

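### No urine sample is guaranteed to precede treatment: the first is scheduled for day 1, while study drug starts on the day of enrollment, which is day 0

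*Combined protocol and SAP*

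**What the plan says.** **Urine.** The research procedures in Section 1.2 (Research Design and Methods) state that "Urine samples will be collected on day 1 and day 14", and Section 1.8 (Specimen Collection) gives the same two days. No other urine collection appears in the supplied text.

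**Day 0.** The day-0 screening visit in Section 1.2 lists research samples "for SARS-CoV-2 RNA will be collected at baseline day 0". These are saliva, swabs and sputum; urine is not among them. The last item of that visit is "Randomize study participant through RedCap".

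**Enrollment.** Under Subject Enrollment in the same section, "RedCap will randomize the patient and a sequence number (subject study ID) will be generated at the time of enrollment". Enrollment and randomization are thus one event, and the visit schedule puts it on day 0.

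**Start of drug.** The Arm 1 description has participants taking Aggrenox twice daily "starting on the day of enrollment for a total of 2 weeks along with standard care". The Treatment Plan repeats it: "starting on the day of enrollment for a total of 2 weeks + standard care". The visit schedule, however, heads the block after screening as a treatment period covering days 1 to 14, and lists no drug administration on day 0.

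**Endpoint.** Secondary endpoint 10 (Section 1.2, B. Endpoints) reads "if feasible urine will be analysed for markers of tubular injury IL-18, kidney injury molecule-1 [KIM-1", followed by further injury, inflammation and repair markers. It names no time point, baseline or change. In the same list, the inflammatory markers and the ordinal scale are explicitly compared with baseline on day 0.

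**The concern.** Two urine samples, one at the start and one at the end of treatment, invite a before-and-after comparison. That comparison needs a first sample that treatment cannot have touched. Only the Aggrenox arm receives study drug, so a first sample taken after dosing carries any early drug effect in that arm alone. Subtracting the first sample, or adjusting for it, then removes part of the effect of interest, or adds to it if the early effect runs the other way.

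An early effect cannot be dismissed on the protocol's own pharmacology. Section 1.7 gives peak plasma levels at about 2 hours for dipyridamole and 0.63 hours for aspirin, so a sample on the day after a first dose comes from an exposed patient. Section 4.7, in its drug-interaction text, attributes reduced renal blood flow to aspirin's inhibition of renal prostaglandins. This makes an early movement in kidney markers possible; it does not show that one occurs or how large it would be.

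What is at stake is a clean change score or baseline adjustment for endpoint 10. No primary or power claim depends on it.

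**Working it through.** The plan gives no figure on this point, so there is none to reproduce. The check is a timeline count, followed by the algebra of the contrasts that could be used.

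**Step 1: which day is enrollment?** Randomization is an item of the day-0 visit, and Subject Enrollment places randomization at enrollment. Enrollment is therefore day 0.

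**Step 2: doses before the first urine.** The inputs are twice-daily dosing for 14 days and a first urine on day 1. The count assumes that the sample is taken before the second dose of day 1.

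| Reading | Treatment days | Doses before day 1 | Doses on day 1 before the sample | Total before first urine |
|---|---|---|---|---|
| Drug starts on the day of enrollment (Arm 1 text, Treatment Plan) | 0 to 13 | 1 to 2 | 0 to 1 | 1 to 3 |
| Drug starts on day 1 (treatment-period heading) | 1 to 14 | 0 | 0 to 1 | 0 to 1 |

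Across both readings the range is about 0 to 3. Under the first, the day-1 sample follows dosing. Under the second, it falls on the first dosing day and may come before or after the dose, because the text does not say. Neither reading guarantees a pre-dose sample. The reading also decides whether day 14 is the last treatment day or the day after it, a second reason to settle the matter.

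**Step 3: effect on each possible contrast.** Let *E* be the true between-arm difference in a marker at day 14, and *fE* the difference already present in the day-1 sample.

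- Day-14 levels alone: *E*. The first sample does not enter.
- Day-14 minus day-1 change: *E* − *fE* = (1 − *f*)*E*.
- Day-14 level adjusted for the day-1 value with slope *b*: *E* − *b*(*fE*) = (1 − *bf*)*E*.

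The documents give no value for *f* and nothing from which to derive one. If *f* = 0, all three agree. If *f* > 0 (with *b* > 0 and *f* below 1), the second and third are too small. If *f* < 0, meaning an early transient effect in the opposite direction, they are too large. No numerical range for the bias can be defended from the documents.

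**The case against.** A reader might infer that the Aggrenox arm certainly lacks a pre-treatment urine sample and that the between-arm comparison for endpoint 10 is therefore biased. The documents do not support that, for three reasons.

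1. **The first dosing day is in conflict.** The treatment-period heading covers days 1 to 14, medication compliance is reviewed in that block, and the stated 14 days of treatment fit it. On that reading the day-1 urine could be pre-dose. This objection stands against certainty. It does not supply the missing safeguard, because no instruction puts the sample ahead of the dose.

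2. **No analysis is specified that the timing would harm.** Endpoint 10 defines no change score, and the day-1 urine is nowhere called a baseline. Sections 1.5 and 6.1 adjust for the minimization variables, not for a baseline marker value. The timing of the first sample does not bias a randomized comparison of day-14 levels. This stands in full. The problem is confined to analyses that use the day-1 value, although those are the natural use of a two-sample schedule.

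3. **The governing schedule was not seen.** Section 1.10 refers all procedures to the study flow table in Appendix A, which is not in the supplied text and might list a day-0 urine or pre-dose timing. This limit is real. If it does so, Sections 1.2 and 1.8, which agree with each other on day 1 and day 14, would still need to be brought into line with it.

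It is also fair that this is the last of ten secondary endpoints, conditional on feasibility, in a study that calls itself a pilot.

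**Conclusion.** The point holds as a minor one. The supplied text neither schedules nor guarantees a pre-treatment urine sample. About 0 to 3 doses may come before the first sample in the Aggrenox arm, depending on how the conflict over the first treatment day is resolved and on the hour of collection. A day-1 to day-14 change, or adjustment for the day-1 value, could be biased by an unknown amount that may be zero. The day-14 comparison between randomized arms is untouched.

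This rests on enrollment being day 0, which Section 1.2 supports by placing randomization at that visit; on a day-1 sample taken before that day's second dose, for the upper count of 3; and on Appendix A not adding a pre-dose urine sample.

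**What to change.** 1. Reconcile the first treatment day between the Arm 1 and Treatment Plan wording and the treatment-period heading in Section 1.2. Which day it should be is for the investigators to decide.
2. Amend the urine lines in Sections 1.2 and 1.8 so that the first sample is collected at the day-0 visit, with the other baseline research samples, before the first dose and in both arms. Check Appendix A for consistency.
3. Record collection time relative to the first dose. Section 1.8 already records the date and time of each specimen, so only the first-dose time is needed in addition.
4. State the contrast for endpoint 10, and state that no post-dose sample serves as a baseline. For patients without a scheduled pre-dose sample, use day-14 levels as the between-arm contrast in both arms. Do not restrict the analysis to patients whose first sample happened to precede a dose: only the Aggrenox arm has a dose to precede, so that selection would act on one arm.

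The number of samples does not change. The cost is a same-day urine collection and its transport to the freezer, added to an already busy screening day. If enrollment is too far advanced to move the sample, items 3 and 4 are still worth doing where first-dose times can be recovered, because Section 1.8 puts specimen analysis at the end of the study or accrual period.
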